#### 17. Groups

Group allocation for the AN-69 Oxiris membrane or the standard AN-69 membrane will be done by randomization before starting each CRRT treatment. This process will be performed through Epidat 4.2 software by one of the researchers from the Instituto Nacional de Ciencias Médicas y Nutrición, Salvador Zubirán.

#### 18. Recruitment

All patients who meet inclusion criteria and without the presence of exclusion criteria, requiring CRRT due to AKI and COVID-19 disease, will be included. At the Instituto Nacional de Ciencias Médicas y Nutrición, Salvador Zubirán, the capacity for critically ill patients with invasive mechanical ventilation is of 44 beds.

At the Instituto Nacional de Enfermedades Respiratorias, the ICU possesses a capacity of 16 beds with invasive mechanical ventilation.

In these two areas where the recruitment will take place.

Thirty-six patients will be included. The number of participants from each institute will vary and it will depend on the subjects fulfilling the inclusion criteria. Each Institute is expected to contribute 50% of the total required subjects.

#### 19. Follow-up variables

- Laboratory tests obtained from the electronic medical records during the hospital admission.

- Time on mechanical ventilation.

- Time and dose of vasopressor.

- Length of ICU-stay.

- Days of hospital stay.

- Recovery of kidney function (defined as dialysis-free at 28, 60, and 90 days after discharge).

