## 8. Literature review

On March 11th, 2020 the World Health Organization declared the new coronavirus disease (COVID-19) as a global pandemic. In México, approximately 35% of COVID-19 positive patients require hospital admission and 4.4% do it in the intensive care unit. Acute kidney injury (AKI) in mild to moderate COVID-19 disease seems to be infrequent; in contrast, critically ill patients or those with a severe disease develop AKI in up to 30% of the cases and nearly half of them will need renal replacement therapy in the form of continuous renal replacement therapy (CRRT). AKI in this context seems to be a marker of multiorgan dysfunction and it produces increased mortality in this population.

Multiple mechanisms of AKI in COVID-19 disease have been proposed: direct injury into podocytes and proximal convoluted tubule cells, organ-organ interactions (lung-kidney axis), and cytokine storm. Of them, the severe cytokine-induced injury seems to be the strongest mechanism participating in AKI in this group of severely ill patients with CRRT need thus representing a valuable therapeutic option.

Lately, extracorporeal blood purification therapies have been proposed as a therapeutic tool for cytokine removal in patients with sepsis (prototype of cytokine storm model). Therefore, new membranes with hemoadsorption capacity have been developed and are now commercially available. The first group of membranes used for patients with sepsis and inflammatory systemic response syndrome was high cut-off semipermeable membranes (HCO) followed by non-selective adsorbent membranes, semi selective semipermeable membranes (AN69), and last highly selective semipermeable (especially those with endotoxin and cytokine adsorption, such as AN69-Oxiris). Although these membranes were designed to improve inflammation, they can also be used as a regular filter in CRTT in patients with AKI. These products can be purchased in our country and internationally but there is scant evidence supporting its efficacy to improve clinical outcomes in patients with overt sepsis.

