#### 12. Outcomes

Outcomes:

-Primary outcome: to establish the superiority of treatment with the AN69-Oxiris membrane to sustain a similar MAP with a lower requirement of norepinephrine (at least 0.1 micrograms/kg/min) after 72 hours of treatment initiation, in patients with COVID-19 associated AKI requiring CRRT, compared to the usage of a standard AN69 membrane.

-Secondary outcomes:

- To evaluate the effectiveness of the AN69-Oxiris membrane in reducing interleukin serum levels (IL 6, IL 10, and TNF alpha).
- To demonstrate the advantage of the AN69-Oxiris membrane in decreasing 28-day mortality from the start of CRRT.
- To establish the safety of using the AN69-Oxiris membrane in patients with AKI and COVID-19 infection who require CRRT.
- To examine the efficacy of the AN69-Oxiris membrane in reducing the length of ICU stay compared to the use of a conventional membrane (standard AN-69) in critically ill patients with COVID-19 associated AKI and CRRT requirement.

Variables:

Acute kidney injury. Elevation in serum creatinine or decrease in the urinary output according to what is established in the KDIGO guidelines.

Mean arterial pressure. MAP is considered as the perfusion pressure for organs and, a value greater than 60 mmHg is adequate to maintain perfused the organs of an average person. The mean arterial pressure will be registered, either obtained through a peripheral arterial line (calculated from the area under the curve of the arterial pressure graph) or the non-invasive monitor using the oscillometric method.

Furosemide stress test: This term refers to a furosemide bolus of 1 mg/kg (ideal body weight) with subsequent measurement of urine output after 2 hours. It is considered negative when the urine output during this interval is less than 200 ml.

Safety variables:

\* Clotting of the circuit: it is defined as the presence of clots in the circuit lines and/or filter, which condition rise in the transmembrane, pre-filter, or post-filter pressures, warranting a change of the filter.

\* Allergic reaction: the sudden presence of erythema or rash at any time after starting CRRT treatment.

\* Access bleeding: the occurrence of continuous bleeding at the vascular access insertion site any time after the start of CRRT treatment.

\* Catheter-related bloodstream infection: the presence of any microorganism in blood cultures drawn from catheter's lumen.

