### 13. Sample size

The main outcome considered for this study is the mean dose of norepinephrine at 72 hours after CRRT initiation. Previous studies consider that a difference of at least 0.10 micrograms/kg/min without changes in the MAP, in the intervention group compared to the control group, is a meaningful difference to detect.

Standard deviation for norepinephrine: 0.10 micrograms/kg/min.

Type of test: Two-tailed, with a confidence level of 95% and a statistical power of 80%. Solving the following equation to calculate the sample size using the comparison of 2 means method; a total of 34 patients, 17 within each group, is required. If a 10% loss is assumed, the final sample size will be 36 individuals, 18 in the intervention group (AN69 Oxiris membrane), and 18 in the control group (standard AN69 membrane).

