#### 16. Statistical analysis

Descriptive statistics will be used with measures of central tendency and dispersion of the data according to their distribution. The distribution of the variables will be analyzed with the Kolmogorov-Smirnov "Z" test. For categorical variables, frequencies and percentages will be used. For continuous variables with normal distribution, the mean and standard deviation will be shown. In contrast, the median and interquartile range will be used for continuous variables with an abnormal distribution.

The Student's t-test will be used to compare continuous variables between the two groups, in case of a normal distribution. The Mann-Whitney U-test will be performed for groups with an abnormal distribution. The analysis of data inside the same group at different time intervals (baseline vs 72 h) will be carried out using the Student's t-test, Wilcoxon sum of ranks, or McNemar's test, as appropriate.

Multivariate analysis for mortality will be performed using Cox proportional hazards, adjusted for the baseline SOFA score. Statistical analysis and graphs will be obtained using SPSS 19.0 software (Chicago, IL) and Graphpad Prism 5 software (San Diego, Ca), respectively. A p-value <0.05 will be considered significant. An intention-to-treat analysis will be pursued.

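### Kidney recovery is timed from discharge with no rule for deaths, so a by-arm report would naturally cover only patients discharged alive and could mislead

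*Combined protocol and SAP*

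**What the plan says.** Section 19 (Follow-up variables) ends its list with "Recovery of kidney function (defined as dialysis-free at 28, 60, and 90 days after discharge". It does not say whether hospital or ICU discharge is meant, although the same list records ICU stay and hospital stay separately.

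Kidney recovery is not among the goals (section 10) or the primary and secondary outcomes (section 12).

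Two secondary outcomes in section 12 bear on it. One is mortality, with its own time origin: "To demonstrate the advantage of the AN69-Oxiris membrane in decreasing 28-day mortality from the start of CRRT". The other is a shorter ICU stay with Oxiris.

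Section 16 (Statistical analysis) says "An intention-to-treat analysis will be pursued" and, for deaths, "Multivariate analysis for mortality will be performed using Cox proportional hazards, adjusted for the baseline SOFA score". For comparisons between arms it says "The Student's t-test will be used to compare continuous variables between the two groups", with a rank test as the alternative. It names no between-arm test for a yes/no variable such as recovery. No section makes being alive part of the recovery definition, counts death as non-recovery, or treats death as a competing event.

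**The concern.** Randomisation makes the arms comparable at the moment of allocation. A variable that exists only from discharge onward is measured in a subset chosen later, by survival. If the membrane affects survival, the patients discharged alive in the two arms need not be alike. An arm that keeps sicker patients alive, some of them still on dialysis, can look worse for kidney recovery because it did better on mortality.

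Timing is a second issue. If one arm is discharged earlier, its 28-day check falls sooner after the kidney injury than the other arm's, even with equal mortality.

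Recovery is the only listed follow-up variable defined by kidney outcome in a trial of acute kidney injury, so it could well be reported by arm.

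**Working it through.** **Plan's own figure.** None is given for kidney recovery. The only computed figure is the sample size for norepinephrine, from "a difference of at least 0.10 micrograms/kg/min without changes in the MAP" and "Standard deviation for norepinephrine: 0.10 micrograms/kg/min", two-sided 5%, 80% power. With difference/SD = 0.10/0.10 = 1, the t-based calculation gives 16.7, so 17 per arm and 34 in total, as stated. Nothing below changes it. I use the stated final size of 36, 18 per arm.

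**Who can be assessed.** The check dates are D + 28, D + 60 and D + 90, where D is the time from randomisation to discharge.
- A patient who dies before discharge has no D, so none of the three dates exists.
- For patients discharged alive, D differs, so the checks fall at different times after randomisation.
- A patient who dies after discharge but before a check has dates but no stated score.

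**How many.** Section 8 says of acute kidney injury that "it produces increased mortality in this population", but gives no rate. The mortality before discharge, m, is therefore assumed. Number assessable = 36 × (1 − m):

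| Assumed m | Per arm (of 18) | Total (of 36) |
|---|---|---|
| 30% | 12.6 | about 25 |
| 50% | 9.0 | 18 |
| 60% | 7.2 | about 14 |

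**What it can do to a comparison.** Recovery among patients discharged alive = (alive and dialysis-free) / (18 − deaths). Recovery in all randomised patients = (alive and dialysis-free) / 18. All counts are assumed, with every survivor taken as discharged.

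| Case | Arm | Deaths | Alive, dialysis-free | All randomised | Discharged alive |
|---|---|---|---|---|---|
| A | Control | 9 | 8 | 8/18 = 44% | 8/9 = 89% |
| A | Oxiris | 5 | 8 | 8/18 = 44% | 8/13 = 62% |
| B | Control | 9 | 8 | 8/18 = 44% | 8/9 = 89% |
| B | Oxiris | 5 | 10 | 10/18 = 56% | 10/13 = 77% |
| C | Control | 9 | 8 | 8/18 = 44% | 8/9 = 89% |
| C | Oxiris | 9 | 8 | 8/18 = 44% | 8/9 = 89% |

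- Case A: no difference in all randomised patients becomes 27 points against Oxiris (89% − 62%).
- Case B: 11 points in favour of Oxiris (10/18 − 8/18) becomes 12 points against it (8/9 − 10/13).
- Case C: with equal deaths and equal recovery, the two denominators agree that there is no difference.

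**The case against.** The strongest reply is that the plan never states the comparison at issue. Recovery is the last item in a list of follow-up variables, no test is named for it, and neither a survivors-only denominator nor a by-arm contrast is written. That is correct. The team could report recovery over all 18 patients per arm with deaths as not recovered, and the general intention-to-treat sentence would fit that. What is written is the time origin. The restriction to patients discharged alive is what that origin naturally produces when no death rule is given.

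A reader might go further and infer that the plan prescribes a biased survivors-only comparison, or that it contradicts itself. The documents support neither. Timing mortality from the start of CRRT and dialysis status from discharge gives two variables with two origins, which is not a contradiction. The intention-to-treat sentence does not say how an outcome is scored after death. Dialysis status after discharge is also a legitimate descriptive question about survivors.

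Nor should a reader infer from case B that reversal is likely. Its counts were chosen to reverse the sign, and neither contrast in it is distinguishable from chance (Fisher's exact p about 0.62 for 8/9 against 10/13, and about 0.74 for 8/18 against 10/18). Section 8 notes that earlier small human studies of these membranes found no effect on mortality, and section 15 excludes patients with SOFA above 11 or an expected survival under 72 hours. These points limit what can be said about size. They do not remove the weakness, because the trial itself aims to lower mortality and shorten ICU stay.

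**Conclusion.** The point holds as a cheap improvement to a stated definition. Counting from discharge ties the variable to an event after randomisation that some patients never reach and that others reach at different times, and no section says how deaths are scored. A by-arm report on this definition can mislead if the membrane affects survival or length of stay.

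The size in this trial cannot be estimated. The illustrations rest on assumed deaths and recovery counts, and with equal mortality the survivor distortion may be absent, although the timing problem can remain. Reading discharge as hospital discharge is also an assumption. If ICU discharge is meant, the same argument applies to deaths in the ICU.

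Importance is modest. The primary outcome, the listed secondary outcomes and the sample size are unaffected.

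**What to change.** In section 19, define kidney recovery as being alive and dialysis-free at days 28, 60 and 90 after randomisation (or after the start of CRRT, matching the mortality outcome). Assess it in all randomised patients, with death at any time before the check counted as non-recovery. In section 16, add that it is reported as a risk difference with a 95% CI. Dialysis-free status among patients discharged alive can stay as a descriptive result, labelled as such, with discharge specified as hospital or ICU.

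The sample size and the number of scheduled checks per patient do not change. The change does cost more than wording. Check dates move earlier and some fall during admission, the observation window after discharge becomes shorter, and patients who die before discharge now enter the denominator. The question also changes, from status after discharge to status at fixed days in everyone randomised.

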#### 20. Samples

Serum samples from included patients will be stored, labeled, and frozen at -70 °. After the recruitment period, the samples will be thawed for the measurement of serum interleukins.

These samples will be used only for the determination of the aforementioned markers and will be discarded after 3 years of study initiation.

